**Statement of Compliance to protocol, GCP and applicable regulatory guidelines:**

This trial will be conducted in compliance with the protocol, ISO 14155, the International Conference for Harmonization Good Clinical Practice E6 (ICH-GCP), the Declaration of Helsinki, and all applicable regulatory requirements.

## CHANGE HISTORY

Version	Originator	Description of Change(s) and Section Number(s) Affected	Date
1.0	[name]	Original Protocol	27 Nov 2017
2.0	██████████	Correction to exclusion #13 and addition of electronic consent in pre-screening. Amended reasons for registering study on clinicaltrials.gov in section 21.	01 Dec 2017
3.0	██████████	Added note in Section 3.3 and Synopsis regarding exclusion of potential subjects with allergy or sensitivity to ingredients.  Updated Section 6.2 to include “alternative sponsor approved product” for ancillary supplies	20 Dec 2017

## SYNOPSIS

Protocol Title	Clinical Evaluation of two marketed artificial tears in non-contact lens wearing patients
Sponsor	JJV, [name]
Clinical Phase	Post Marketing, Phase 4
Trial Registration	This study will be registered on ClinicalTrials.gov based on the following: the study will be utilizing marketed products to assess endpoints related to comfort.
Test Article(s)	Two artificial tears products: 

• blink® intensive TRIPLE ACTION 3 in 1 eye drops (Test)

• Systane® BALANCE eye drops (Control)

Treatment dosage	Dosage: Instill 1-2 drops OU at least three times a day.
Objectives	The primary objective of this study is to gain clinical insights of the products with respect to ocular comfort after one week of use.
Study Endpoints	Primary endpoint: VAS comfort score Secondary endpoint: OSDI score Other endpoints: DEQ-5, LipiView II®, NITBUT, ocular physiology, subject's reported ocular symptoms, adverse events

Study Design	
The study design is a randomized, double-masked, bilateral, 2 treatment × 2 period, dispensing, 4-visit study:
 
Visit 0: pre-screening with completion of DEQ-5
 
Visit 1: Baseline and eligibility, randomization. Dispense first eye drop solution. LipiView II® measurement at approx.5 mins, 30 mins, 1 hour, and 2 hours post-drops. VAS comfort.
 
Study drops used at least 3x per day for 7-9 days.
 
Visit 2: One-week follow-up - Questionnaires, LipiView II®, NITBUT, slit lamp findings. VAS comfort.
 
Washout period: 7-9 days (habitual artificial tear usage)
 
Visit 3: Baseline, confirm eligibility, dispense second eye drop solution. LipiView II® measurement at approx..5 mins, 30 mins, 1 hour, and 2 hours post drop. VAS comfort.
 
Study drops used at least 3x per day for 7-9 days.
 
Visit 4: One-week follow up, Questionnaires, ®, NITBUT, slit lamp findings, final evaluation. VAS comfort.
 
See the Summary of Visits table at the end of the synopsis for the schematic of the study visits and procedures of main observations.

Sample Size	Approximately 60 non-contact lens wearing subjects are targeted to be enrolled and approximately 50 subjects are targeted to complete the study.
Study Duration	The study will last approximately 3 months and include a 2-month enrollment period.
Anticipated Study Population	Non-contact lens wearers 18-69 years of age with occasional symptoms of dry eye and/or signs based on a DEQ-5 score of greater than 6.

Eligibility Criteria
	
Potential subjects must satisfy all the following criteria to be enrolled in the study:
 
 
1. Subjects must be at least 18 years of age and no more than 69 years of age (inclusive)
 
2. Subjects must be non-contact lens wearers
 
3. Subjects must have a DEQ-5 score of >6 at either Visit 0 (pre-screen) or Visit 1 (screening)
 
4. Subjects must achieve visual acuity of 20/30 (equivalent to 0.18logMAR) or better in each eye, either unaided or best corrected
 
5. Subjects must possess a functional/ usable pair of spectacles and bring them to the visit (only if applicable - to the investigators discretion).
 
6. Subjects must read, understand, and sign the Statement of Informed Consent
 
7. Subjects must appear able and willing to adhere to the instructions set forth in this clinical protocol
 
 
Potential subjects who meet any of the following criteria will be excluded from participating in the study:
 
 
1. Currently pregnant or breast-feeding
 
2. Diabetes
 
3. Any ocular or systemic allergies or disease which may interfere with the clinical trial (at the discretion of the investigator).
 
4. Any systemic disease, autoimmune disease, or use of medication which may interfere with the clinical trial (at the discretion of the investigator),
 
5. Any infectious diseases (e.g. hepatitis, tuberculosis) or a contagious immunosuppressive disease (e.g. HIV), by self-report
 
6. Any Grade 3 or greater biomicroscopy findings (this includes, corneal edema, corneal staining, corneal vascularization, conjunctival injection, tarsal abnormalities, bulbar injection) on the FDA classification scale
 
7. Any active ocular abnormalities/conditions that may interfere with the clinical trial (this includes, but not limited to, chalazia, recurrent styles, pterygium, infection, etc).
 
8. Any corneal distortion due to previous rigid gas permeable lens wear, surgery or pathology.
 

-----------------------------	--

[figure not shown]
9. History of any ocular or corneal surgery (e.g. RK, PRK, LASIK)
10. Participation in any pharmaceutical or medical device related clinical trial within 14 days prior to study enrollment.
11. History of binocular vision abnormality or strabismus.
12. Habitual wearers of soft contact lenses within the past 1 month or rigid gas permeable lens within the past 3 months
13. Current habitual use of Prescription Only Medication (POM) to treat dry eye or ocular dryness symptoms that would interfere with the clinical study (at the discretion of the investigator)
14. Employees of investigational clinic (investigator, coordinator, and technician etc) or family members of an employee of the clinical site by self-report.

In addition to the above criteria, patients with any allergy or sensitivity to ingredients that this product may contain (liposomes, sodium hyaluronate, vitamin E polyethylene glycol succinate (TPGS), polyethylene glycol 400 (PEG 400), disodium edetate, polyhexanide methylbiguanide, propylene glycol, boric acid, dimyristoyl phosphatidylglycerol, edetate disodium, hydroxypropyl guar, mineral oil, polyoxyl 40 stearate, polyquaternium-1, sorbitan tristearate, sorbitol, hydrochloric acid and/or sodium hydroxide) should not participate in the study.

Disallowed Medications/Interventions	Current habitual use of Prescription Only Medicines (POM) to treat dry eye or ocular discomfort, ocular steroids, or any medication (RX or OTC) that would interfere with the clinical study (at the discretion of the investigator).
Measurements and Procedures	VAS Scale Comfort, OSDI, DEQ-5, ocular physiology, LipiView II®, and safety parameters.
Microbiology or Other Laboratory Testing	None
Study Termination	The occurrence of one or more Unanticipated Adverse Device Effect (UADE), or any SAE where relationship to study agent cannot be ruled out, will result in stopping further dispensing investigational product. In the event of a UADE or SAE, the Sponsor Medical Monitor may unmask the treatment regimen of subject(s) and may discuss this with the Principal Investigator before any further subjects are enrolled.
Ancillary Supplies/ Study-Specific Materials	BlueDot Saline Pods (or other sponsor-approved material), FluStips
Principal Investigator(s) and Study Institution(s)/Site(s)	A full list of Principal Investigators, clinical sites, and institutions is kept separately from the Study Protocol and is included in the study Trial Master File.

Figure 1: Study Flowchart

## COMMONLY USED ABBREVIATIONS AND DEFINITIONS OF TERMS

ADD	Plus Power Required For Near Use
ADE	Adverse Device Effect
AE	Adverse Event/Adverse Experience
BCVA	Best Corrected Visual Acuity
BSCVA	Best Spectacle Corrected Visual Acuity
CE	Conformité Européene
CFR	Code of Federal Regulations
COAS	Complete Ophthalmic Analysis System
COM	Clinical Operations Manager
CRA	Clinical Research Associate
CRF	Case Report Form
CRO	Contract Research Organization
CT	Center Thickness
CTP	Clinical Technical Procedure
D	Diopter
DMC	Data Monitoring Committee
eCRF	Electronic Case Report Form
EDC	Electronic Data Capture
ETDRS	Early Treatment Diabetic Retinopathy Study
FDA	Food and Drug Administration
GCP	Good Clinical Practice
HIPAA	Health Insurance Portability and Accountability Act
IB	Investigator's Brochure
ICF	Informed Consent Form
ICH	International Council for Harmonization
IDE	Investigational Device Exemption
IEC	Independent Ethics Committee
IRB	Institutional Review Board
ISO	International Organization for Standardization
ITT	Intent-to-Treat
JJV	Johnson & Johnson Vision, Inc.
LC	Limbus Center
LogMAR	Logarithm of Minimal Angle of Resolution
MedDRA ®	Medical Dictionary for Regulatory Activities
MOP	Manual of Procedures
NIH	National Institutes of Health
OD	Right Eye
OHRP	Office for Human Research Protections
OHSR	Office for Human Subjects Research
OS	Left Eye
OSDI	Ocular Surface Disease Index
OU	Both Eyes
PD	Protocol Deviation
PHI	Protected Health Information
PI	Principal Investigator
PIG	Patient Instruction Guide
PQC	Product Quality Complaint
PRO	Patient Reported Outcome
QA	Quality Assurance

QC	Quality Control
SAE	Serious Adverse Event/Serious Adverse Experience
SAP	Statistical Analysis Plan
SAS	Statistical Analysis System
SD	Standard Deviation
SOP	Standard Operating Procedure
UADE	Unanticipated Adverse Device Effect
USADE	Unanticipated Serious Adverse Device Effect
VA	Visual Acuity

## 1. INTRODUCTION AND BACKGROUND

It is estimated that over 16 million US adults have been diagnosed with dry eye. Artificial tears are often used to treat symptoms of ocular dryness and discomfort. Most of the major artificial tear companies have some type of lipid product to address lipid deficient tear films, however JJV CEH does not currently have a lipid-like drop in our portfolio. Additionally, JJV acquired TearScience Q3 2017 to address Meibomian gland disease resulting in lipid deficiencies.

This study will be conducted at a single clinical site (University of Manchester) in the United Kingdom (UK) and will include two marketed (CE marked) artificial tears (blink® intensive TRIPLE ACTION 3 in 1 and Systane® BALANCE) to gain clinical insights with respect to ocular comfort after 1 week of use. By exploring a lipid-like drop addition to the CEH portfolio it would continue to live into the JJV Eye Health Mission.

### 1.1. Name and Descriptions of Investigational Products

The products used in this clinical study are two CE marked/approved artificial tears eye drops:

- blink® intensive TRIPLE ACTION 3 in 1 eye drops (Test)
- Systane® BALANCE eye drops (Control)

### 1.2. Intended Use of Investigational Products

The products are marketed products, available over the counter (without a prescription). They will be used as indicated on-label to reduce symptoms of ocular dryness. Subjects will be required to use the 1-2 drops in both eyes at least 3 times a day. There is no maximum number of drops per day.

The proposed intended use of all the study artificial tears are subjects with symptoms of ocular dryness. For this study, we will use a cut off DEQ-5 score of 6. A score of greater than 6 indicates the presence of ocular discomfort and/or dryness and subject eligibility.

### 1.3. Summary of Findings from Nonclinical Studies

Not Applicable - Marketed products only.

### 1.4. Summary of Known Risks and Benefits to Human Subjects

The following risks/adverse events can be associated with using artificial tears, in general:

- There may be less comfort than when the drop was first placed on the eye.
- The eyes may burn, sting and/or itch.
- There may be a feeling of something in the eye (foreign body, scratched area).

- There may be the potential for some temporary impairment due to peripheral infiltrates, peripheral corneal ulcers and corneal erosion.
- There may be the potential for other physiological observations, such as local or generalized edema, corneal neovascularization, corneal staining, injection, tarsal abnormalities, iritis and conjunctivitis, some of which are clinically acceptable in low amounts.
- There may be excessive watering, unusual eye secretions, or redness of the eye.
- Poor visual acuity, blurred vision, rainbows or halos around objects, photo-phobia, or dry eyes may also occur if the drops are used continuously or for too long a time.

There is no direct benefit to the subject for participating in the study, although they will be able to try out new artificial tears. The information from this study will aid if the further development and design of new artificial tears.

For the most comprehensive clinical information regarding the artificial tears refer to the package inserts (Appendix C).

### **1.5. Relevant Literature References and Prior Clinical Data Relevant to Proposed Clinical Study**

All artificial tears evaluated in this study are CE marked/approved and marketed products. Refer to package inserts (Appendix C) for additional information.

## **2. STUDY OBJECTIVES, ENDPOINTS AND HYPOTHESES**

### **2.1. Objectives**

The primary objective of this study is to gain clinical insights of the products with respect to ocular comfort after 1 week of use.

### **2.2. Endpoints**

#### **Primary Endpoint:**

The primary endpoint is ocular comfort score at 1-week follow-up using Visual Analogue Scale (VAS) of comfort. VAS of comfort consists of a vertical line which represents continuous scale from 0 (extremely uncomfortable) to 100 (extremely comfortable).

#### **Secondary endpoint:**

The secondary endpoint is subjective assessment of dry eye symptoms at 1-week follow-up using Ocular Surface Disease Index (OSDI®) instrument. The OSDI® is assessed on a scale of 0 to 100, with higher scores representing greater disability. The index demonstrates sensitivity and specificity in distinguishing between normal subjects and patients with dry eye disease. The OSDI® is a reliable instrument for measuring dry eye disease (normal, mild to moderate, and severe) and effect on vision-related function OSDI® questionnaire.

#### **Other Endpoints:**

- DEQ-5 score at 1-week follow-up
- LipiView II® lipid layer measurement at 5 min, 30 min, 60 min, and 120 min post drop instillation.
- Non-invasive tear break-up time (NITBUT)

- Expanded corneal staining (██████████)
- Slit-Lamp findings (██████████)
- Subject's reported ocular symptoms (██████████)
- Adverse events

DEQ-5 questionnaire is a subset of Dry Eye Questionnaire (DEQ) items that discriminate across self-assessed severity and various diagnoses of dry eye. It is comprised of 5 items: frequency of watery eyes, discomfort, and dryness (0-4 scale) and late day discomfort and dryness intensity (0-5 scale). The DEQ-5 score is the sum of scores for frequency and late day intensity of dryness and discomfort plus frequency of watery eyes. DEQ-5 scores greater than 6 suggest dry eye is present and results greater than 12 may require further testing to rule out Sjögren's syndrome.

### 2.3. Hypotheses

This is a pilot study and all the hypotheses are exploratory in nature.

#### Primary hypothesis:

The Test eye drop is superior to the Control eye drop with respect to ocular comfort as measured using VAS comfort at 1-week follow-up

#### Secondary hypothesis:

The Test eye drop is superior to the Control eye drop in reducing dry eye symptoms as measured using OSDI at 1-week follow-up.

## 3. TARGETED STUDY POPULATION

### 3.1. General Characteristics

The study populations will be healthy non-contact lens wearers between 18-69 years of age from a single site in the UK.

### 3.2. Inclusion Criteria

Potential subjects must satisfy all the following criteria to be enrolled in the study:

1. Subjects must be at least 18 years of age and no more than 69 years of age (inclusive)
2. Subjects must be non-contact lens wearers
3. Subjects must have a DEQ-5 score of >6 at either Visit 0 (pre-screen) and/or Visit 1 (screening).
4. Subjects must achieve visual acuity of 20/30 (equivalent to 0.18 logMAR) or better in each eye, either unaided or best corrected.
5. Subjects must possess a functional/usable pair of spectacles and bring them to every visit (only if applicable - to the investigators discretion).
6. Subjects must read, understand, and sign the Statement of Informed Consent.
7. Subjects must appear able and willing to adhere to the instructions set forth in this clinical protocol

### 3.3. Exclusion Criteria

Potential subjects who meet any of the following criteria will be excluded from participating in the study:

1. Currently pregnant or breast-feeding.
2. Diabetes.
3. Any ocular or systemic allergies or disease which may interfere with the clinical trial (at the investigator's discretion).
4. Any systemic disease, autoimmune disease, or use of medication which may interfere with the clinical trial (at the investigator's discretion).
5. Any infectious diseases (e.g. hepatitis, tuberculosis) or a contagious immunosuppressive disease (e.g. HIV), by self-report
6. Any Grade 3 or greater biomicroscopy findings (this includes, corneal edema, corneal staining, corneal vascularization, conjunctival injection, tarsal abnormalities, bulbar injection) on the FDA scale
7. Any active ocular abnormalities/conditions that may interfere with the clinical trial (this includes, but not limited to, chalazia, recurrent styles, pterygium, infection, etc)
8. Any corneal distortion due to previous rigid gas permeable lens wear, surgery or pathology
9. History of any ocular or corneal surgery (e.g. RK, PRK, LASIK)
10. Participation in any pharmaceutical or medical device related clinical trial within 14 days prior to study enrollment.
11. History of binocular vision abnormality or strabismus.
12. Habitual wearers of soft contact lenses in the past 1 month or rigid gas permeable lens within the past 3 months
13. Current habitual use of Prescription Only Medicines (POM) to treat dry eye or ocular discomfort, ocular steroids, or any medication (RX or OTC) that would interfere with the clinical study (at the discretion of the investigator.)
14. Employees of investigational clinic (investigator, coordinator, and technician etc) or family member of an employee of the clinical site by self-report.

In addition to the above criteria, patients with any allergy or sensitivity to ingredients that this product may contain (liposomes, sodium hyaluronate, vitamin E polyethylene glycol succinate (TPGS), polyethylene glycol 400 (PEG 400), disodium edetate, polyhexanide methylbiguanide, propylene glycol, boric acid, dimyristoyl phosphatidylglycerol, edetate disodium, hydroxypropyl guar, mineral oil, polyoxyl 40 stearate, polyquaternium-1, sorbitan tristearate, sorbitol, hydrochloric acid and/or sodium hydroxide) should not participate in the study.

### 3.4. Enrollment Strategy

Study subjects will be recruited from the University of Manchester, UK's subject database and/or utilizing Independent Ethics Committee (IEC) or Institutional Review Board (IRB) approved materials.

## **4. STUDY DESIGN AND RATIONALE**

### **4.1. Description of Study Design**

The study design is a randomized, double-masked, bilateral, 2 treatment × 2 period, dispensing, 4-visit study.

After a pre-screening assessment, eligible subjects will be invited to attend an initial visit. At study Visit 1, subjects will be consented and screened for inclusion/exclusion criteria. If a subject is found to meet all eligibility criteria, they will be dispensed with the first artificial tears eye drops based on the randomization scheme; otherwise, the subject will be discontinued from the study. After dispensing of the first eye drop solution; NITBUT, LipiView II® measurement at taken at approximately 5 mins, 30 mins, 1 hour, and 2 hours post drop

Subjects will be dispensed with their randomly assigned eye drops and instructed to use them OU at least 3 times a day over a 7-9 day period. The follow-up evaluation (Visit 2) will occur 7-9 days after the initial visit. At this visit questionnaires, LipiView II®, NITBUT, slit lamp findings will be captured.

After completion of Visit 2, there is a 7-9 day washout period during which subjects may use their habitual products, if any, but they will be advised not use any eye drops on the day of Visit 3

Following the washout period, the subject returns for Visit 3 and is dispensed with the second randomized eye drop with NITBUT, LipiView II® measurements at approximately 5 mins, 30 mins, 1 hour, and 2 hours post drop. Subjects will be dispensed with their second randomly assigned eye drops and instructed to use them OU at least 3 times a day over a 7-9 day period. Visit 4 takes place 7-9 days after visit 3, at which questionnaires, LipiView II®, NITBUT, slit lamp findings, final evaluation will take place.

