### **4.2. Study Design Rationale**

Crossover designs are a well-established cost-effective study design in which subjects are exposed to multiple treatments during different time periods. This design was considered because patient-specific factors that might affect comfort are well controlled. A washout period of 7-9 days was implemented between each treatment exposure to reduce any potential carry-over effect that may bias the results.

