### 5.2. Masking

This is a double-masked study where subjects, investigators are masked to the identity of the eye drops during the study period. Every attempt will be made to keep the other clinical trial personnel involved in the study (e.g., Data management, Biostatistician) unaware of the identity of the test articles.

The identity of the investigational products will be masked by over labeling the eye drop bottles with a label containing the study number, expiration date and the randomization codes. Only the personnel involved in the over labeling and the Statistician generating the randomization scheme will have access to the decode information translating the randomization codes into Test and Control treatment. The medical monitor will also have access to the decode information in case breaking the mask is necessary for the urgent medical treatment of a subject.

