2.9.	Tear film lipid layer thickness	Record the tear film lipid layer thickness, OD & OS	Measure per LipiView II® II manufacturer instruction (Appendix D)
2.10.	Habitual tear film stability (Medmont)	Record the tear film stability (NITBUT), OD & OS	NITBUT Medmont Work Aid (Appendix E)
2.11.	Slit Lamp Biomicroscopy	The FDA slit lamp classification scale will be used to grade the findings.  (All ocular AE's must be followed to resolution)  If the clearance of the fluorescein needs to be expedited, preservative-free rewetting drops or saline may be instilled.	
2.12.	Expanded Sodium Fluorescein Corneal Staining	Corneal Staining Assessment (1.0 scale units) will be assessed using a more detailed scale for internal purposes only.	
2.13.	Exit Visual Acuity	Record the distance high contrast visual acuity to the nearest letter (OD, OS, and OU) with their habitual spectacle correction in place (or unaided if applicable).	Eurolens Research SOP

Visit 2: Follow-up on drop #1			
Step	Procedure	Details	
2.14.	Washout instructions	Instruct subject they may use any habitual drops during their washout of 7-9 days	

### VISIT 3

The subjects must present to visit 3 wearing their habitual spectacles (if applicable) having not used any artificial tears that day.

Visit 3: Dispense Drop #2			
Step	Procedure	Details	
3.1.	Adverse Events and Concomitant Medications Review	Review any changes to the subject's medical history or concomitant medications from the previous study visit. Record any changes, and any adverse events.	
3.2.	Artificial Tear Use	The subject will be asked about their artificial tear use.	
3.3.	Subject Reported Ocular Symptoms	Subjects will respond to a verbal open-ended symptoms questionnaire.	
3.4.	DEQ-5 Questionnaires	The subject will respond to the DEQ-5 Questionnaires.	
3.5.	OSDI questionnaire	The subject will respond to the OSDI questionnaire.	
3.6.	VAS Questionnaire	The subject will respond to the VAS comfort questionnaire	
3.7.	Entrance visual acuity	Record the distance high contrast visual acuity to the nearest letter (OD, OS, and OU) with their habitual spectacle correction in place (or unaided if applicable).	Eurolens Research SOP
3.8.	Tear film lipid layer thickness	Record the tear film lipid layer thickness, OD & OS	Measure per LipiView II® II manufacturer instruction (Appendix D)
3.9.	Habitual tear film stability (Medmont)	Record the tear film stability (NITBUT), OD & OS	NITBUT Medmont Work Aid (Appendix E)

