### 2.3 *Precautions*

The following patient conditions may affect the interferometry assessment of a patient's tear film using LipiView II:

- **Use of ophthalmic drops such as artificial tear lubricants, ointments, and medications.** Advise patients not to instill oil-based ophthalmic drops (e.g., Soothe®, Restasis®, Systane Balance®) for at least 12 hours prior to device use and not to instill ointments for at least 24 hours prior to device use. Wait at least 4 hours after instillation of all other ophthalmic drops prior to device use.
- **Soft or rigid contact lens wear.** Advise patients to remove contact lenses at least 4 hours prior to device use.
- **Use of oil-based facial cosmetics around the eye.**
- **Eye rubbing.**
- **Recent swimming in a chlorinated pool.** Advise patients not to swim for at least 12 hours prior to device use.
- **Any ocular surface condition** that affects the stability of the tear film. These conditions include disease, dystrophy, trauma, scarring, surgery, or abnormality.

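### Habitual users of either study drop are not excluded, and the only described mask is an over-label, so recognition of a familiar drop may bias the self-rated endpoints

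*Combined protocol and SAP*

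**What the plan says.** **Washout.** Section 4.1 states that "there is a 7-9 day washout period during which subjects may use their habitual products, if any". The Synopsis describes the washout as "7-9 days (habitual artificial tear usage", and step 2.14 in section 7.2 reads "Instruct subject they may use any habitual drops during their washout of 7-9 days". None of these excepts the study products. Section 4.2 gives the purpose: "A washout period of 7-9 days was implemented between each treatment exposure to reduce any potential carry-over effect that may bias the results".

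**Eligibility.** Section 1.2 says of the two drops: "The products are marketed products, available over the counter (without a prescription". None of the 14 exclusions in 3.3 and no disallowed medication in section 9 names habitual use of either. The nearest text is exclusion 13, which ends with "any medication (RX or OTC) that would interfere with the clinical study (at the discretion of the investigator"; the Synopsis version of exclusion 13 covers prescription-only medicines alone. Subjects bring their habitual drops to Visit 1 and are asked about tear use at step 1.4. No eligibility rule, stratification, model term or sensitivity analysis uses the answer.

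**Masking.** Section 5.2: "The identity of the investigational products will be masked by over labeling the eye drop bottles". Section 6.4 adds that commercial cartons are one permitted outer pack. The documents describe no matching of bottle, appearance or feel, and the ingredient lists in 6.1 differ.

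**LipiView.** The device instructions in Appendix D (2.3 Precautions) name the Control product among oil-based drops not to be instilled "for at least 12 hours prior to device use and not to instill ointments for at least 24 hours prior to device use". The protocol asks only that no drops be used on the day of Visits 1 and 3.

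**The concern.** The trial recruits people with dry-eye symptoms and expects some of them to use artificial tears already. If one of those products is a study drop, the subject meets it again in one period under an over-label and meets an unfamiliar drop in the other. Subjects normally instil the drops themselves (step 1.16), and both the primary endpoint (VAS comfort) and the secondary endpoint (OSDI) are their own ratings. A regular user who recognises the drop may rate it up or down for reasons unrelated to its effect.

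A crossover with randomised order protects against effects tied to the period. It does not protect against an effect tied to the product. What is at stake is the superiority comparison in 14.5 and 14.6, and the predictive probabilities in 14.7 that are meant to inform later trials.

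**Working it through.** **1. The plan's own figure.** Inputs from 14.2: 50 completers, paired test, Δ of 5 or 10, ρ of .30, .50 or .80; 5% error rate from 14.4, taken as two-sided.

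SD of the within-subject difference = 25 × √(2(1 − ρ)):
- ρ = .50: 25 × √1 = 25, so SE = 25/√50 = 3.54
- ρ = .80: 25 × √0.4 = 15.8, so SE = 15.8/√50 = 2.24

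Power from the noncentral t with 49 df is 21.6, 28.4 and 59.2% for Δ = 5, and 64.9, 79.2 and 99.2% for Δ = 10. All six cells of Table 4 reproduce. They do so only if 25 is the SD; section 14.2 calls it a variance, which would give about 100% power throughout. That wording is a separate matter. SD 25 is used below.

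**2. Size of a recognition shift.** Let f_T and f_C be the shares of habitual Test and Control users, and b the VAS points by which a recognised drop is favoured. A habitual Test user's Test − Control difference moves by +b and a habitual Control user's by −b, in either sequence. The mean difference moves by

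(f_T − f_C) × b.

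The documents give none of these quantities, so the inputs are assumptions. The last two columns give the chance that the lower limit of a two-sided 95% interval exceeds 0 when there is no true difference. They use n = 50 and a paired t-test as a stand-in for the Bayesian model; the nominal value is 2.5%.

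| Net share × points | Shift | ρ = .50 | ρ = .80 |
|---|---|---|---|
| 5% × 5 | 0.25 | 2.9% | 3.2% |
| 10% × 10 | 1.0 | 4.6% | 6.4% |
| 20% × 10 | 2.0 | 8.0% | 13.9% |

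If habitual Control users are the more numerous, the sign reverses: a true Test benefit of 5 points would appear as 5 − 0.25 = 4.75 down to 5 − 2 = 3. If f_T = f_C with equal preference, the shift is 0.

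**3. The washout.** A habitual Control user is on Control before Visit 1 and again before Visit 3, whichever sequence is assigned. Let h1 and h2 be whatever residue of habitual use remains at the end of periods 1 and 2.
- Test/Control: (T + h1) − (C + h2) = (T − C) + (h1 − h2)
- Control/Test: (T + h2) − (C + h1) = (T − C) − (h1 − h2)

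With 25 completers in each sequence, the residue cancels from the average. With 30 and 25, the ends of Table 1's range, a simple average keeps (30 − 25)/55 = 0.09 of (h1 − h2). The model has no period term to absorb that. However, h1 and h2 follow the same habitual state and a further 7-9 days on the assigned drop, so their difference should be small.

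**4. Cost of removing such users.** If 5, 10, 20 or 30% of the 50 completers are removed and not replaced, n is 48, 45, 40 or 35. Power at Δ = 10, ρ = .50 falls from 79.2% to 77.5, 74.7, 69.4 or 63.3%. At Δ = 5, ρ = .80 it falls from 59.2% to 57.4, 54.6, 49.6 or 44.4%.

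**5. LipiView.** A drop at 23:00 before a 09:00 visit satisfies the day-of-visit rule but is only 10 hours before the reading, against the 12 hours in Appendix D. This touches the pre-drop lipid readings at Visits 1 and 3, not the VAS or OSDI.

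**The case against.** The case against is substantial, and part of it stands.

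- **Carry-over.** A reader might infer that a washout spent on a study drop biases the Test-Control comparison. The documents do not support that. Returning to habitual drops puts each subject in the same state before both periods, so the residue largely cancels when sequences are balanced. What remains is that, for these subjects, the washout is not the separation of exposures that 4.2 describes.
- **Size and direction.** A reader might infer a shift of several points against the Test by supposing that only Control users are present. Nothing supports setting habitual Test users to zero; only the difference between the shares counts. At the low end of the range the false-success chance barely moves.
- **Frequency.** A reader might infer that many subjects are affected. Sections 4.1 and 7.2 speak of habitual drops only conditionally and give no share for any brand. They also do not say whether the over-labelled drops can be told apart.
- **Existing safeguards.** Exclusions 4 and 13 and section 9 let the investigator exclude interfering medication, study bottles are collected at step 2.3, and step 3.2 asks about tear use again. These help case by case, but none is a rule about the study products.
- **Pilot status.** Section 2.3 calls all hypotheses exploratory. That lowers the stakes. It does not remove them, because the plan still declares superiority and may use the data for scientific materials (section 21).

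**Conclusion.** The gap is real and modest. Habitual users of either study product can enter, the described mask is an over-label, and any recognition bias in the VAS and OSDI would follow the product and survive randomised order. Under the assumed range the mean VAS difference moves by 0.25 to 2 points, against planning differences of 5 and 10; it is zero if shares and preferences are equal. This rests on an assumed net share and an assumed preference, on every habitual user recognising the drop, and on SD 25. The OSDI shift has the same form but cannot be sized, because the plan gives no OSDI variability.

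The contradiction between the washout rule and its stated purpose should be acknowledged, but it is not a material source of bias in the primary contrast. The LipiView timing conflict is real and separate, and confined to that endpoint. Overall this is a cheap improvement worth making, not a flaw that invalidates the design.

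**What to change.** Add to 3.3 and the Synopsis an exclusion for current habitual use of either study product, checked at step 1.4 against the bottles that subjects already bring. Because the washout allows habitual products, this also keeps both study drops out of it.

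Ideally ask about brand at the optional Visit 0 too. Step 1.4 comes after consent, and 4.3 counts consent as enrolment with a ceiling of 60. If 10 or 20% of 60 were excluded at that stage, 6 or 12 places would be used, leaving 54 or 48 before drop-out against a target of 50 completers.

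The cost is some screen failures, a slightly narrower population and an added question in the pre-screen. It is small only if such users are few; if they are common, replacements must be recruited to avoid the power loss shown above.

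At a minimum, record the habitual brand and prespecify a sensitivity analysis of VAS and OSDI without these users. That keeps eligibility as it is but loses precision in the restricted analysis.

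Separately, reconcile the day-of-visit wording for Visits 1 and 3 with the Appendix D interval. The exclusion alone does not settle this, because the precaution covers other oil-based drops as well.
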